RRT Fidelity. We will be able to electronically track whether reports go out and whether they are timely/accurate. In addition, although we do not have a scalable way to track outreach attempts for 6,000 subscribers in Study 2, we will carefully document implementation processes and meet monthly with CareSource and intervention agencies, hear their experiences, offer feedback, and help problem-solve challenges. We will keep structured implementation process notes from these meetings for further analysis. Provider names will be included in the notes. All data from the implementation process feedback will be securely stored in REDCap. No names or identifiers will be used in any published works and will be accessible only to authorized research staff. Testing our service engagement mechanism will also help to elucidate steps in the causal chain (i.e., from the reports, to services provided, to suicide attempts).

Assignment to “intervention” and “control” conditions in the two studies is independent: participants may receive Intervention-Intervention, Intervention-Control, Control-Intervention, or Control-Control. Participants will be followed for 6 months following jail release using claims data.

C4. Data Analysis

Twelve months of historical (i.e., prior to arrest) and six months of prospective (i.e., after release) jail and Medicaid claims data will be extracted from CareSource’s Jail-Medicaid database for each participating subscriber for all measures, including demographics, diagnoses, suicide attempts, service use, number of arrests, dates of jail bookings/releases, and days incarcerated. Each eligible subscriber will be followed for 6 months following the index release from jail using claims data. CareSource will provide a limited dataset to the P50 Center (at MSU) that will be de-identified and analyzed by Center statisticians. Because these statisticians are employed by Brown University, an IAA will be established with both MSU and Brown University.

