For Aim 1, we will assess total number of subsequent attempts using the already-developed Mental Health Research Network (MHRN) algorithm for extracting MT suicide attempt information from claims data.^{10-12,48-58} The main effectiveness analysis is planned as a comprehensive model (i.e., including all 43,000 subscribers) evaluating Study 1 and Study 2 intervention effects, which provides optimal power and the ability to test interactive effects of interventions. All analyses will covary baseline (i.e., past year) values of dependent variables, and will use days incarcerated in the 6 months after the index jail release as an offset. **MT suicide attempts.** The main analysis framework will be logistic regression with the cumulative risk of a claims-data-identified suicide attempts requiring medical treatment over six months post-release as the outcome. We will secondarily use a negative binomial model and a count outcome for the number of MT suicide attempts. Our models will include robust standard errors due to clustering at the agency level. We will adjust for study month, and include indicator variables reflecting: (1) Study 1 intervention condition (i.e., CC or CAU); (2) inclusion in Study 2; (3) Study 2 intervention condition (i.e., RRT or Control). The ***hypothesis that the Study 1 intervention (CC) reduces suicide attempts*** is evaluated with magnitude and significance of parameter estimate associated with random assignment to the Study 1 intervention. The ***hypothesis that the Study 2 intervention (RRT) reduces suicide attempts*** is tested with the parameter estimate associated with exposure to the level 2 intervention. ***The hypothesis that the addition of flags and recommendations to provide SPI*** for individuals with past 12 months claims data identified suicide attempts (one component of the Study 2 intervention) ***will further reduce suicide attempts*** will be tested through the interaction between past history of suicide attempt and being in the Study 2 intervention condition. Identical analyses will be conducted for the other outcomes (all count outcomes): all cause injury and poisoning, outpatient BH visits, calls to CMS line, suicide-related ED visits/hospitalizations, and returns to jail detention. ***Exploratory.*** We will evaluate the interaction of Study 1 and Study 2 interventions by including an interaction term of the two indicators. ***Moderators.*** We will test sex, race/ethnicity, past suicide attempt (y/n), past 6-month BH visit (y/n), past 12-month arrest (y/n), area Deprivation Index,⁵⁹⁻⁶⁰ Mental Health Professional Shortage Area (HPSA)

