Outcome analysis. Suicide attempts as well as service utilization outcomes will be assessed using CareSource's Jail-Medicaid data, which includes Medicaid claims, information on jail booking and release, and other data. As in our past and current studies, this will not be human subjects data because the dataset will not contain personal identifiable information. CareSource will prepare a deidentified dataset that will be made available to authorized research staff through the secure MSU server. Although dates are included in the claims data, all dates relating to the patient, including date of birth, visit dates, dates of labs performed, will be randomly shifted to a fabricated set of dates by CareSource prior to being sent to the research staff. For instance, if a patient's actual visit date was 10/15/2020, CareSource will generate a random date (e.g., 01/30/2001). This will allow us to calculate date and time ranges without using actual patient identifiers.

B. Recruitment and Consent Procedures

Study 1 (Caring Contacts)

Focus Groups:

Provider Focus Groups: Providers will be recruited from the 12 BH agencies via flyers posted in the agencies and on the Internet/social media (e.g., Facebook, LinkedIn). We anticipate recruiting up to 10 providers to provide feedback during each of the focus groups. The initial focus group will be aimed at designing the CC message, while the follow-up focus group will target feedback and problem-solving directed at the use of the CC letters during the study intervention.

Subscriber Focus Groups: Subscribers will be recruited through methods including the use of flyers posted in BH agencies frequented by CareSource subscribers, posting flyers on the Internet/social media, and outreach to participants from a previous study who have given permission to be contacted for future research. Similar to providers, we anticipate recruiting up to 10 subscribers to participate in each of the focus groups (1 initial; up to 2 follow-up).

CC Letters:

After development of the CC letter through stakeholder input in the initial focus groups, CareSource subscribers randomized to the CC group will be mailed CC letters by CareSource. Because this study involves the use of retrospective claims data, individual patients will not be consented for participation. Due to the retrospective nature of the data and the large population, written or verbal consent is not feasible.

Study 2 (Reports, Re-engagement, and Training)

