Potential risks due to loss of confidentiality will be minimized by having all information collected and handled by research staff trained to deal appropriately with sensitive clinical issues. All research personnel will receive training in research ethics. All information will be treated as confidential material and will be available only to authorized research staff. All paper-based materials, if applicable, will be kept in locked files. In addition, the University research servers maintain secure environments for storing and processing clinical data that adhere to or exceed HIPAA principles. Therefore, we anticipate the proposed data collection and analysis procedures will pose minimal risk. Only authorized members of the research team will have access to the data. CareSource will provide the P50 Center (at MSU) with a limited datafile that will be de-identified by P50 Center (Brown University-based) statisticians. The Internal Privacy Department at CareSource will review and approve all data de-identification procedures to ensure compliance with the Safe Harbor Method as well as all internal agency protocols prior to the release of any deidentified data for research purposes. Any results reported with the project will be reported in aggregate. Additional data management and security steps are included in the Data Safety and Monitoring Plan.

D3. Data Safety Monitoring Plan

The study investigators will be responsible for implementing and maintaining quality assurance and quality control systems for this study. Written standard operating procedures will be used to guide the research. The PIs (Drs. [name] and [name]) and research staff at their institutions will meet weekly to review study progress, including recruitment, procedures, and unanticipated problems. The protocol will be reviewed and approved by the investigators' IRBs prior to study start. All protocols and procedures will be reviewed with participants (i.e., focus group, providers) prior to study involvement.

Unanticipated problems related to participation in the study will be reported to the PIs or delegated research staff for the duration of the study. The PIs will have the front-line responsibility for identifying potential unanticipated problems experienced by study participants, adjusting the study procedures accordingly, and reporting the experience.

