For focus groups/implementation process notes (for which we have identifiable data), the PIs will ensure that information on any adverse effects on provider participants are reported to the IRB/DSMB. If any unanticipated problems are detected, these will be submitted to the respective IRBs and DSMB within 72 hours. The Principal Investigators will be responsible for tracking these reports and relaying them as required to their IRBs.

For Caring Contacts and RRT, CareSource will provide a limited datafile to P50 Center statisticians who will generate a de-identified analytic dataset with aggregated, clinic-level data that will be used by the study team to analyze study findings. Similar to studies conducted in the Mental Health

Research Network, service connection and suicide-related outcomes for these 43,000 individuals are evaluated through claims data. Standard reporting and monitoring “adverse events” as typically defined (i.e., patient death, hospitalization, etc.) in real time is not possible because: (1) claims data lag, and (2) data are aggregated and de-identified. However:

1. All study interventions are either standard of care (reach out to individuals after jail release to see if they need additional mental health or substance use treatment) and we are providing a systematized way to do it (through Caring Contacts or weekly reports to agencies) or are considered suicide prevention best practices (assessment with the C-SSRS and intervention with SPI, the only evidence-based suicide prevention intervention for the target population). Therefore, it seems appropriate to evaluate aggregate outcomes of these system-level efforts to use evidence-based practices.
2. Study interventions take place over 12 months. Because of the lag in claims data (~3 months) and the need to de-identify and integrate datasets to be sent to the PIs, it is not possible for us to have real-time access to the data. However, we will take two steps to provide safety information to the DSMB in a timely way:
 - a. We will have the Data and Safety Monitoring Board (DSMB) review the study prior to the start of the study, and then review extant safety data at 6, 9, and 12 months after the start of the study.

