All paper-based materials, if applicable, will be kept in locked files. In addition, Butler Hospital and Michigan State University (MSU) research servers maintain secure environments for storing and processing clinical data that adhere to or exceed HIPAA principles. Therefore, we anticipate the proposed data collection and analysis procedures will pose minimal risk. Only authorized members of the research team will have access to the data. A CareSource will provide the P50 Center (at MSU) with a limited datafile that will be de-identified by P50 Center (Brown University-based) statisticians. The Internal Privacy Department at CareSource will review and approve all data de-identification procedures to ensure compliance with the Safe Harbor Method as well as all internal agency protocols prior to the release of any deidentified data for research purposes. Any results reported with the project will be reported in aggregate.

2. Plan to Destroy Identifiers or Justification for Retaining Identifiers:

The relevant PHI for this waiver is the claims data that will be access and extracted by CareSource. For the CC letters and claims data extraction, all patient identifiers will be maintained by CareSource until all data collection and quality assurance procedures are completed. Once all study-relevant tasks are completed, identifiers will be deleted.

3. Assurances that the PHI will not be Re-used or Disclosed:

Data collected during this study will be accessed by study-relevant research personnel only. No unauthorized use of the data will be allowed for any reason and no PHI will be re-used or disclosed.

5B. Could the research be practicably conducted without a waiver? YES NO

5C. Could the research be practicably conducted without access to and use of the PHI? YES NO

5D. PHI is only needed for activities preparatory to research YES NO

6) DESCRIPTION OF PHI TO BE COLLECTED UNDER WAIVER

No PHI will be collected for the CC letters and assessment of study outcomes via claims data. Authorized CareSource study staff will access subscriber claims data that have been randomly selected for study inclusion. CareSource will have access to the subscriber claims data, but none of the data exported for analysis and shared with study staff outside of CareSource will contain PHI.

7) ADVERTISEMENTS

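### The protocol's data-flow statements contradict each other, and under its date-shifting rule the RRT term of the Aim 1 model cannot be fitted as planned

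*Combined protocol and SAP*

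**What the plan says.** **The model.** Section C4 (Data Analysis, Aim 1) plans one logistic model on all 43,000 subscribers: "We will adjust for study month, and include indicator variables reflecting" Study 1 arm, membership of Study 2 and Study 2 condition. It also uses past-year values of the outcome, days incarcerated after release as an offset, and robust standard errors by agency. Section C2 (Training behavioral health providers) starts the four agency cohorts at Months 4, 6, 8 and 10.

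**Dates.** Section 3.A (Outcome analysis) has CareSource prepare the de-identified file. All dates relating to the patient "will be randomly shifted to a fabricated set of dates by CareSource prior to being sent to the research staff". The stated benefit is limited to intervals: "This will allow us to calculate date and time ranges without using actual patient identifiers". Section 6 adds that "none of the data exported for analysis and shared with study staff outside of CareSource will contain PHI".

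**A different route.** The opening of section C4 says: "CareSource will provide a limited dataset to the P50 Center (at MSU) that will be de-identified and analyzed by Center statisticians". Sections D1 (CC Letters), D2 and 5A repeat this as a "limited datafile that will be de-identified by P50 Center (Brown University-based) statisticians".

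**Record level.** Section D3 says the Center statisticians will "generate a de-identified analytic dataset with aggregated, clinic-level data that will be used by the study team to analyze study findings". Later in D3, analyzed participant data are held under numerical codes, and the DSMB reviews cases by study month.

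**The concern.** In a stepped-wedge comparison, exposure and time move together. Whether a subscriber counts as RRT or control depends on the agency and on the true month of the index release. The same month is needed to separate the RRT effect from any change in attempt rates over the year. A file whose dates have been moved at random for each person supports neither step, unless month or RRT status was attached beforehand.

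The limited-file route might supply real dates, but the documents do not say which fields that file carries. If it carries real dates, that conflicts with section 3.A, where CareSource shifts dates before release and real dates are treated as identifiers, and with section 6, where nothing leaving CareSource contains PHI. So either the analyst lacks an input to the model, or the data-protection statements are inaccurate. Section 5A has CareSource delete identifiers once study tasks are complete, and after that the true month could not be recovered.

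**Working it through.** **1. What each part of the model needs, set against section 3.A.**

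- CC arm: allocated 1:1 by subscriber, so no calendar information is needed.
- Past-year outcome counts, days incarcerated and attempts within six months: intervals relative to booking or release. These survive if all of a person's dates move together, which the stated purpose of the shift implies.
- Study month of index release: calendar position, which a person-specific shift removes.
- RRT status at release: agency code plus calendar position, so also lost unless derived first.

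Section 3.A does not say whether the shift is per person or common to everyone. A common shift would keep relative month. The worked example is of a single patient's date and suggests a per-person shift.

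**2. Record level.** 43,000 − 6,000 = 37,000 subscribers (37,000 / 43,000 = 86%) fall outside the 12 agencies. A file aggregated by those agencies has no natural row for them, so it cannot be the file for the section C4 model.

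**3. How closely RRT is tied to time.** Assume 12 release months, four cohorts and even numbers in each cohort-month.

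- RRT cohort-months: 9 + 7 + 5 + 3 = 24. Control: 3 + 5 + 7 + 9 = 24.
- Mean month under RRT: (72 + 63 + 50 + 33) / 24 = 218 / 24 = 9.083.
- Mean month under control: (6 + 15 + 28 + 45) / 24 = 94 / 24 = 3.917.
- Difference: 5.167 months. Correlation of month with RRT status: 0.75.

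**4. Bias if RRT status is known but month is not.** With no true RRT effect and attempt odds changing by a factor r per month, the apparent odds ratio is about r^5.167. The protocol gives no trend, so r is an assumption.

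- r = 0.99: 0.95
- r = 0.98: 0.90
- r = 1.01: 1.05
- r = 1.02: 1.11

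The fall that would by itself produce the planning value of 0.87 is 1 − 0.87^(1/5.167) = 2.7% per month.

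**5. Check by model.** I fitted the logistic model to expected counts (37,000 outside and 6,000 inside the agencies, spread evenly; baseline risk 0.05; CC odds ratio 0.89; no clustering; the same trend inside and outside the agencies). With no RRT effect and month omitted, the trends in step 4 give 0.949, 0.901, 1.053 and 1.108. With month included, the RRT odds ratio returns to 1.00 each time. The CC odds ratio is 0.89 with or without month. For a true RRT odds ratio of 0.87 and no trend, the standard error of the log odds ratio is 0.131 with month and 0.126 without, so keeping month costs little precision.

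The protocol has no figure of its own on this point to reproduce. Its 88.3% power for RRT is a separate matter, and nothing here rests on it.

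**The case against.** The best reply is that nothing is shown to be lost. Section C4 gives the limited file to the Center statisticians and has them analyze it, and D1, D2, D3 and 5A describe the same route. In D3 the clinic-level file is made by those statisticians from the limited file, so aggregation comes after they already hold it. The coded participant data and the DSMB review by study month imply that someone keeps both subscriber records and month. Identifiers stay with CareSource until quality assurance is complete, so a deficient extract could be reissued.

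Most of this stands, and it rules out two stronger readings. A reader might infer that the release rules remove the data the primary model needs. The documents support only that they contradict one another. A reader might also infer that the CC analysis cannot be run on individuals. That would follow only if the clinic-level file were all the statisticians had, which C4 and D3 do not say.

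It is also fair to say that the biased odds ratios need an intermediate case that the documents do not describe: whoever derives RRT status before the shift has month in hand and could pass it on.

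What the reply leaves open is the conflict itself. No section lists month or RRT status as retained, and the limited-file route cannot carry real dates without contradicting sections 3.A and 6.

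**Conclusion.** The point holds as an unresolved contradiction with a specific consequence for RRT. On section 3.A's rule, read as a per-person shift, the RRT term cannot be fitted as planned. With neither month nor RRT status supplied, the effect is not estimable. With status but not month, an assumed fall in odds of 1% to 2% per month gives a spurious odds ratio of about 0.95 to 0.90, and an equal rise gives about 1.05 to 1.11, which would mask a benefit. For comparison, the planned effect is 0.87.

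These sizes rest on assumed trends, even accrual and no clustering. They show sensitivity and do not predict bias in this trial. It would be wrong to read the 2.7% per month figure as evidence that the hypothesised effect is a time trend, because it was solved backward from 0.87. The CC contrast is unaffected by loss of calendar month.

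**What to change.** 1. Reconcile sections C4, 3.A, D1, D2, D3, 5A and 6. State who de-identifies, at which step, and who holds which file.
2. Require these fields to be derived before any date shift and kept in the analysis file: study month of index release, agency and cohort code, RRT status at release, CC arm, past-year counts, days incarcerated, and days from release to each event.
3. State that the Aim 1 analysis uses one record per subscriber, and confine clinic-level aggregation to reporting or to files shared beyond the statisticians.

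Design, sample size and model are unchanged. The cost is protocol wording, a few derived fields in the CareSource extract, and approval by the CareSource privacy department. That approval is a real step, because study month has to be squared with the Safe Harbor standard named in D2 and 5A. It should be settled before the extract is specified, and in any case before CareSource deletes identifiers.

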All paper-based materials, if applicable, will be kept in locked files. In addition, Butler Hospital and Michigan State University (MSU) research servers maintain secure environments for storing and processing clinical data that adhere to or exceed HIPAA principles. Therefore, we anticipate the proposed data collection and analysis procedures will pose minimal risk. Only authorized members of the research team will have access to the data. A CareSource will provide the P50 Center (at MSU) with a limited datafile that will be de-identified by P50 Center (Brown University-based) statisticians. The Internal Privacy Department at CareSource will review and approve all data de-identification procedures to ensure compliance with the Safe Harbor Method as well as all internal agency protocols prior to the release of any deidentified data for research purposes. Any results reported with the project will be reported in aggregate.

2. Plan to Destroy Identifiers or Justification for Retaining Identifiers:

The relevant PHI for this waiver is the claims data that will be access and extracted by CareSource. For the CC letters and claims data extraction, all patient identifiers will be maintained by CareSource until all data collection and quality assurance procedures are completed. Once all study-relevant tasks are completed, identifiers will be deleted.

3. Assurances that the PHI will not be Re-used or Disclosed:

Data collected during this study will be accessed by study-relevant research personnel only. No unauthorized use of the data will be allowed for any reason and no PHI will be re-used or disclosed.

5B. Could the research be practicably conducted without a waiver? YES NO

5C. Could the research be practicably conducted without access to and use of the PHI? YES NO

5D. PHI is only needed for activities preparatory to research YES NO

6) DESCRIPTION OF PHI TO BE COLLECTED UNDER WAIVER

No PHI will be collected for the CC letters and assessment of study outcomes via claims data. Authorized CareSource study staff will access subscriber claims data that have been randomly selected for study inclusion. CareSource will have access to the subscriber claims data, but none of the data exported for analysis and shared with study staff outside of CareSource will contain PHI.

7) ADVERTISEMENTS

Flyers will be used for provider and subscriber recruitment to participate in the focus groups. For the RRT intervention, interested BH agencies have already been identified by CareSource. Information about the study will be provided to the agencies prior to contacting providers about study participation.

8) INFORMED CONSENT FORM (ICF), ASSENT OF MINOR & PARENTAL PERMISSION FORM

✓Consent form(s) are attached. Indicate number of consent(s): 3

Identify each consent: BH_provider_ICF (to consent the behavioral health providers); Focus_Provider_ICF (for providers in focus groups); Focus_Subscriber_ICF (for non-provider participants in focus groups).
